### 5.3.2. Safety Data

Missing values in standard summaries of AEs, laboratory data, vital signs, and ECGs will be imputed according to CaPS.

## 6. ANALYSES AND SUMMARIES

### 6.1. Primary Endpoints

*The effect of varying degrees of hepatic impairment on PK parameters will be assessed by constructing 90% CIs around the estimated difference between each of the Test (hepatic impaired) groups and the Reference (without hepatic impairment) group. A one-way ANOVA will be used to compare the natural log transformed PF-07923568  $AUC_{inf}$ ,  $C_{max}$ , and  $AUC_{last}$ , as data permit, for each of the hepatic impairment groups (Test) to the group without hepatic impairment (Reference). Estimates of the adjusted mean differences (Test /Reference), and corresponding 90% CIs, will be obtained from the model. These will be exponentiated to provide estimates of the ratio of adjusted geometric means (Test/Reference) and 90% CIs for the ratios.*

*Individual PF-07923568 concentrations will be listed and summarized descriptively by nominal PK sampling time and hepatic function group. Individual participant and summary profiles of the concentration-time data (using actual and nominal times, respectively) will be plotted by hepatic function group for total plasma PF-07923568.*

*Box and whisker plots for individual PK parameters ( $AUC_{inf}$ ,  $AUC_{last}$ , and  $C_{max}$ , if data permit) will be constructed by hepatic function group and overlaid with geometric means. PK parameters of PF-07923568 will be summarized descriptively by hepatic function group.*

*Additional analysis using linear regression may be used to analyze the potential relationship between appropriate PK parameters (eg,  $AUC_{inf}$ ,  $AUC_{last}$ ,  $C_{max}$ , if data permit) and hepatic function (eg, serum albumin concentration, PT or T bili). Plots of PK parameters (eg,  $AUC_{inf}$ ,  $AUC_{last}$ ,  $C_{max}$ ) versus hepatic function will be constructed, with a regression line and 90% confidence region included. Estimates of the slope and intercept, together with a 90%*

*CI, and the coefficient of determination (ie, R-squared and adj-R-squared) may be obtained from the model.*

*Additionally, as an exploratory analysis, age and body weight may be explored as additional covariates/factors in the models, as appropriate.*

## **6.2. Secondary Endpoints**

### **6.2.1. Safety Data**

Safety data analyses and summaries are described in [Section 6.6](#).

## **6.3. Other Endpoints**

The plasma concentrations of PF-07923568 will be listed and descriptively summarized by nominal PK sampling time and hepatic function group on the PK Concentration Set.

Individual participant and summary profiles (mean and median plots) of the plasma concentration-time data will be plotted by hepatic function group using actual and nominal times, respectively. Mean and median profiles will be presented on both linear and semi-log scales.

Presentations of concentrations will include:

- A listing of all concentrations sorted by participant ID, hepatic function group and nominal time postdose. The concentration listing will also include the actual times. Deviations from the nominal time will be given in a separate listing.
- A summary of concentrations by hepatic function group and nominal time postdose, where the set of statistics will include n, mean, median, SD, %CV, minimum, maximum and the number of concentrations above the LLQ.
- Median concentrations time plots (on both linear and semi-log scales) against nominal time postdose by hepatic function group (all hepatic function groups on the same plot per scale, based on the summary of concentrations by hepatic function group and time postdose).
- Mean concentrations time plots (on both linear and semi-log scales) against nominal time postdose by hepatic function group (all hepatic function groups on the same plot per scale, based on the summary of concentrations by hepatic function group and time postdose).
- Individual concentration time plots by hepatic function group (on both linear and semi-log scales) against actual time postdose (there will be separate spaghetti plots for each hepatic function group per scale).

- Individual concentration time plots by participant (on both linear and semi-log scales) against actual time postdose [there will be separate plots for each participant (containing all hepatic function groups) per scale].

The plasma PK parameters for PF-07923568 will be summarized descriptively by hepatic function group in accordance with Pfizer data standards on the PK Parameter Set, as data permit. Missing values will be handled as detailed in [Section 5.3.1](#). Each PK parameter (Table 4) will be summarized by hepatic function group and will include the set of summary statistics as specified in Table 5.

**Table 4. Noncompartmental PK Parameters**

PK Parameter	Analysis Scale	PF-07923568
AUC last	ln	A, D
AUC inf *	ln	A, D
C max	ln	A, D
T max	R	D
t 1/2 *	R	D
CL/F*	ln	D
V z /F*	ln	D

Key: A=analyzed using statistical model, D=displayed with descriptive statistics, ln=natural-log transformed, R=raw (untransformed), \*=if data permits

**Table 5. PK Parameters to be Summarized Descriptively by Hepatic Function Group**

Parameter	Summary Statistics
AUC inf , AUC last , C max , CL/F, V z /F	N, arithmetic mean, median, SD, %CV, minimum, maximum, geometric mean and geometric %CV
T max	N, median, minimum, maximum
t 1/2	N, arithmetic mean, median, SD, %CV, minimum, maximum

#### 6.4. Subset Analyses

There are no planned subset analyses.

#### 6.5. Baseline and Other Summaries and Analyses

##### 6.5.1. Demographic Summaries

Demographic characteristics (age, gender, ethnicity, race, weight, height and body mass index) will be summarized by hepatic function group for enrolled population in accordance with the CaPS.

### **6.5.2. Study Conduct and Participant Disposition**

Participants evaluation groups will show end of study participant disposition. Frequency counts will be supplied for participant discontinuation(s) by hepatic function group. Data will be reported in accordance with the CaPS.

### **6.5.3. Concomitant Medications and Nondrug Treatments**

All concomitant medication(s) as well as non-drug treatment(s) will be reported in the listings.

## **6.6. Safety Summaries and Analyses**

All safety analyses will be performed on the Safety Analysis Set.

Safety data will be presented in tabular and/or graphical format and summarized descriptively by hepatic function group, where appropriate.

### **6.6.1. Adverse Events**

Adverse events will be reported in accordance with the CaPS.

Participant discontinuations due to adverse events will be detailed by hepatic function group. Data will be reported in accordance with the CaPS.

### **6.6.2. Laboratory Data**

Laboratory data will be listed and summarized by hepatic function group in accordance with the CaPS.

### **6.6.3. Vital Signs**

Vital sign data will be databased and available upon request.

### **6.6.4. Electrocardiograms**

ECG data will be databased and available upon request.

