9.3.3. Secondary Endpoint Analysis - Safety Analyses

All safety analyses will be performed on the safety population.

AEs, ECGs, BP, pulse rate, and safety laboratory data will be reviewed and summarized on an ongoing basis during the study to evaluate the safety of participants. Any clinical laboratory, ECG, BP, and pulse rate abnormalities of potential clinical concern will be described. Safety data will be presented in tabular and/or graphical format and summarized descriptively, where appropriate, following Sponsor standards.

Medical history and PE and neurological examination information, as applicable, collected during the course of the study, will be considered source data and will not be required to be reported, unless otherwise noted. However, any untoward findings identified on physical and/or neurological examinations conducted during the active collection period will be captured as AEs, if those findings meet the definition of an AE. Data collected at screening that are used for inclusion/exclusion criteria, such as laboratory data, ECGs, and vital signs, will be considered source data, and will not be required to be reported, unless otherwise noted. Demographic data collected at screening will be reported. COVID-19 specific assessments data will be considered source data and will not be required to be reported.

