9.3.3.1. Electrocardiogram Analyses

Changes from baseline for the ECG parameters HR, QTcF, PR interval, and QRS complex will be summarized by treatment and time. The frequency of uncorrected QT values above 500 ms will be tabulated.

The number (%) of participants with maximum post-dose QTcF values and maximum increases from baseline in the following categories will be tabulated by treatment:

Safety QTcF Assessment

| Degree of Prolongation | Mild (ms) | Moderate (ms) | Severe (ms) |
|-------------------------------|------------------|----------------------|--------------------|
| Absolute value | >450-480 | >480-500 | >500 |
| Increase from baseline | | 30-60 | >60 |

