### 3.5. Safety Endpoints

The following data are considered in standard safety summaries (see protocol for collection days, baseline assessment, and list of parameters):

- Adverse events (AE)
- Laboratory data
- Vital signs data
- ECG results

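### The SAP plans no ECG or vital-sign output, although the protocol commits to ECG tables, both are secondary-endpoint components, and the SAP declares no change from the protocol

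*SAP*

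**What the plan says.** Protocol section 3 and SAP 2.2 define the secondary endpoint by four components: treatment-emergent adverse events, laboratory abnormalities, vital signs and ECG parameters.

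Protocol 9.3.3.1 sets out the ECG analysis in detail. Its first commitment reads: "Changes from baseline for the ECG parameters HR, QTcF, PR interval, and QRS complex will be summarized by treatment and time." A second concerns long intervals without rate correction: "The frequency of uncorrected QT values above 500 ms will be tabulated." It also requires the number and percentage of participants in categories of maximum post-dose QTcF and of maximum QTcF increase. Protocol 9.3.3 is more general. It has ECGs, blood pressure and pulse rate reviewed and summarised on an ongoing basis, and adds: "Any clinical laboratory, ECG, BP, and pulse rate abnormalities of potential clinical concern will be described."

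SAP 6.6 then treats the components differently. Adverse events are reported under the sponsor's standards (6.6.1). For laboratory data, "Laboratory data will be listed and summarized by hepatic function group in accordance with the CaPS" (6.6.2). Sections 6.6.3 and 6.6.4 are one sentence each: "Vital sign data will be databased and available upon request" and "ECG data will be databased and available upon request".

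Elsewhere the SAP assumes that summaries will exist. Section 3.5 introduces a list that includes vital signs and ECG results with "The following data are considered in standard safety summaries". Sections 3.5.3 and 3.5.4 define baseline and change from baseline for both. Section 5.3.2 says: "Missing values in standard summaries of AEs, laboratory data, vital signs, and ECGs will be imputed according to CaPS." Under modifications to the protocol's analysis plan, SAP 2.1 records none.

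**The concern.** Keeping data in a database for use on request is retention, not a planned output. Read literally, SAP 6.6.3 and 6.6.4 remove every planned display of two secondary-endpoint components. The rest of the SAP, and its declaration that nothing changed, say that the protocol's analyses still stand. One analyst could program the protocol's ECG tables and another could produce nothing, each citing current text.

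Cardiovascular safety would not be lost altogether, because the data are kept and findings that meet the adverse event definition are reported. What would be lost is the by-group view of changes that never become adverse events. That view matters here for two reasons. Cardiovascular effects are a listed potential risk, with vital-sign and ECG monitoring as the stated mitigation (protocol 2.3.1). Exposure may also rise with impairment, for some similarly cleared compounds more than 2-fold in severe impairment (protocol 4.2).

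**Working it through.** No sample size or error rate is involved. The check sets the passages side by side and then counts what is missing.

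**Commitment against plan**

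| Component | Protocol | SAP 6.6 |
|---|---|---|
| Adverse events | Summarised (9.3.3) | Reported (6.6.1) |
| Laboratory | Summarised, abnormalities described (9.3.3) | Listed and summarised by group (6.6.2) |
| Vital signs | Summarised, abnormalities described (9.3.3) | No output (6.6.3) |
| ECG | As for vital signs, plus three named outputs (9.3.3.1) | No output (6.6.4) |

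Two of four components have no planned output, and none of the three named ECG outputs appears in the SAP.

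**Strength of each conflict.** It is strongest for ECG, because protocol 9.3.3.1 names its outputs without qualification. It is weaker for vital signs, where no specific table is named. The general presentation sentences in protocol 9.3.3 and SAP 6.6 apply only where appropriate, so on their own they could tolerate an omission. That qualifier is absent from protocol 9.3.3.1, from the protocol sentence on describing abnormalities, and from SAP 5.3.2. Protocol 9.3.3 does exempt some ECG and vital-sign data from reporting, but only data collected at screening and used for eligibility.

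**Size of the ECG gap.** Inputs: four parameters (HR, QTcF, PR, QRS); five QTcF categories, namely three absolute (>450-480, >480-500, >500 ms) and two of increase (30-60, >60 ms); four hepatic function groups; and two scheduled post-dose times, 24 h and 120 h. The times are read from a Schedule of Activities table that is broken in extraction, so they are an assumption.

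- Change-from-baseline summaries: 4 parameters × 2 times × 4 groups = 32.
- QTcF category counts: 5 categories × 4 groups = 20.
- In addition, the frequency of uncorrected QT above 500 ms.

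These are table cells, not separate tables. Protocol 9.3.3.1 says by treatment, and there is only one treatment. Taken literally that gives 4 × 2 × 1 = 8 summaries and 5 counts. The by-group reading follows from protocol 9.3.1, which analyses endpoints by hepatic function group, and from SAP 6.6.

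**Would adverse event reporting fill the gap?** Appendix 8's list of ECG findings that may qualify as adverse events, which is not exhaustive, begins for QTcF at >480 ms or a rise of ≥60 ms. The >450-480 ms category lies below that level, and so does the 30-60 ms category except at exactly 60 ms. Two of the five categories would therefore not reliably surface. Under protocol 10.3.1, abnormal safety findings associated with the underlying disease are not adverse events unless more severe than expected, so this route is weakest in Groups 2-4.

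**The case against.** The strongest reply is that the SAP is allowed to do this. Protocol section 9 lets the SAP modify planned analyses and requires an amendment only for major changes to primary endpoint definitions or analyses. The SAP (19 May 2023) is later than the protocol version it cites (23 Feb 2023), and its wording in 6.6.3 and 6.6.4 is explicit. The natural reading may be that the outputs were dropped on purpose and section 2.1 was not updated. That would make this a failure to declare. The permission is real, but a deliberate removal would still contradict SAP 2.1, 3.5 and 5.3.2 and would leave secondary-endpoint components unreported.

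On vital signs, the protocol's ongoing summary can be read as in-study review, and abnormalities can be described in narrative. This softens the vital-sign point without removing it, since SAP 3.5 and 5.3.2 still presume vital-sign summaries.

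The practical loss is also limited, and this part stands:

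- As far as the schedule can be read, no routine post-dose ECG falls near the 5-6 h tmax. With the 7-10 h half-life seen in healthy participants, 120 h is about 12 to 17 half-lives after dosing (120/10 = 12; 120/7 ≈ 17), though impairment may lengthen this. Restored tables would not describe peak exposure.
- The >450-480 ms band is an absolute value. QTcF above 450 ms excludes a participant from Group 1, but the limit is 470 ms in Groups 2-4, so a count in that band partly reflects eligibility. This makes the change-from-baseline summary the more informative display.
- Sites compare each ECG with baseline, and large prolongations trigger repeat tracings (protocol 8.3.3).

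**Conclusion.** The concern holds. Two of the four secondary-endpoint components have no planned SAP output. For ECG this contradicts specific, unqualified protocol commitments; for vital signs it contradicts a general one. In both cases the SAP conflicts with its own sections 3.5 and 5.3.2, while section 2.1 declares no change. The conflict with SAP 6.6 is softer because of its qualifier.

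The cell counts rest on reading the post-dose times as 24 h and 120 h and on summarising by hepatic function group. The conflict between the documents depends on neither. This should be fixed, but it does not touch the primary PK analysis, and adverse event reporting preserves part of the safety picture.

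**What to change.** In SAP 6.6.4, restore the three outputs of protocol 9.3.3.1, stated by hepatic function group and, for the changes from baseline, by time. In SAP 6.6.3, specify a descriptive summary of blood pressure and pulse rate by group and time, using the baseline and change already defined in SAP 3.5.3. The protocol itself names no vital-sign change-from-baseline table, so this is the SAP's to define. In both sections, add the description of abnormalities of potential clinical concern required by protocol 9.3.3.

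If the removal was intended, declare and justify it in SAP 2.1 and bring SAP 2.2, 3.5, 5.3.2 and 6.6 into line. Restoring the outputs fits the secondary-endpoint status of these data better.

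The cost is SAP wording and a few standard descriptive tables on data already collected. Data collection, sample size and the primary analysis do not change.

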## **7. INTERIM ANALYSES**

No formal interim analysis will be conducted for this study. As this is an open-label study, the sponsor may conduct unblinded reviews of the data during the course of the study for the purpose of safety assessment, facilitating PK modeling, and/or supporting clinical development.

Final analysis will follow the official database release. As this will be an open-label study, there is no formal unblinding of the randomization code.

## APPENDICES

### Appendix 1. List of Abbreviations

Abbreviation	Term
%CV	coefficient of variation
AE	adverse event
AUC 24	area under the concentration curve from time 0 to 24 hours
AUC inf	area under the plasma concentration-time curve from time 0 extrapolated to infinite time
AUC inf,u	unbound AUC inf
AUC last	area under the plasma concentration-time curve from time 0 to the time of C last
AUC last,u	unbound AUC last
BLQ	below the limit of quantitation
BP	blood pressure
CaPS	CDISC and Pfizer Standards
CDISC	Clinical Data Interchange Standards Consortium
CI	confidence interval
CL/F	apparent clearance
C last	predicted plasma concentration at the last quantifiable time point
C max	maximum plasma concentration
C max,u	unbound C max
ECG	electrocardiogram
HR	heart rate
k el	terminal phase rate constant
LLQ	lower limit of quantitation
N/A	not applicable
NC	not calculated
ND	not done
NS	no sample
PD	pharmacodynamic(s)
PK	pharmacokinetic(s)
POPPK	population PK
PR	pulse rate
QRS	combination of Q-, R- and S- wave on an electrocardiogram representing ventricular depolarization
QTc	corrected QT interval
QTcF	QTc corrected using Fridericia's formula
RR	respiratory rate
SAP	Statistical Analysis Plan
SD	Standard Deviation
SoA	schedule of activities
SOP	standard operating procedure
t ½	terminal phase half-life

Abbreviation	Term
TEAE	treatment-emergent adverse event
T max	time to reach C max
V z/F	apparent volume of distribution

## Appendix 2. SAS code

An example of the PROC MIXED code is provided below:

```
proc mixed data = tab.pk covtest alpha=0.1;
  class group;
  model l&var = group / S covb alpha=0.1 CL DDFM=KR;
  repeated/ type=un subject=subjid group=group R;
  lsmeans group;
```

```
estimate ' Mild HI vs Without HI'      group -1 1 0 0;
estimate ' Moderate HI vs Without HI" group -1 0 1 0;
estimate ' Severe HI vs Without HI"   group -1 0 0 1;
ods output lsmeans = lsmeans&var;
ods output solutionf = solution&var;
run;

/* Letter assignments for group within the estimate statement above are as follows;
A = Without HI' (Reference);
B = Mild HI (Test1)
C = Moderate HI (Test2)
D = Severe HI (Test3)
*/;
```

An example of the PROC REG code is provided below:

```
proc reg data=tab.pk;
  model l&var=clcr/clb alpha=0.1;
  ods output ParameterEstimates = param&var;
  ods output FitStatistics = fit&var;
  ods output ANOVA = reg&var;
run;
```

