9.3.2.3. Supplementary Analyses

Additional analysis using linear regression may be used to analyze the potential relationship between appropriate PK parameters (eg, AUC_{inf} , AUC_{last} , C_{max} , if data permit) and hepatic function (eg, serum albumin concentration, PT or T bili). Plots of PK parameters (eg, AUC_{inf} , AUC_{last} , C_{max}) versus hepatic function will be constructed, with a regression line and 90% confidence region included. Estimates of the slope and intercept, together with a 90% CI, and the coefficient of determination (ie, R-squared and adj-R-squared) may be obtained from the model.

Additionally, as an exploratory analysis, age and body weight may be explored as additional covariates/factors in the models, as appropriate.

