### 2.1. Modifications to the Analysis Plan Described in the Protocol

None.

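### The SAP's example regression code uses `clcr` as its predictor, where the plan calls for a hepatic function marker

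*SAP*

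**What the plan says.** SAP 6.1 provides for a supplementary regression: "Additional analysis using linear regression may be used to analyze the potential relationship between appropriate PK parameters" and "hepatic function (eg, serum albumin concentration, PT or T bili"). Protocol 9.3.2.3 describes the same analysis and lists its results: "Estimates of the slope and intercept, together with a 90% CI, and the coefficient of determination (ie, R-squared and adj-R-squared) may be obtained". In both documents the regression estimates are optional. The plots of PK parameters against hepatic function are not: both documents commit to producing them, each with a fitted line and a 90% confidence region.

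SAP Appendix 2 gives code for this regression, introduced by "An example of the PROC REG code is provided below". Its MODEL statement is "model l&var=clcr/clb alpha=0.1", and its output requests begin with "ods output ParameterEstimates = param&var;", followed by the fit statistics and the ANOVA table.

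SAP 2.1, headed "Modifications to the Analysis Plan Described in the Protocol", records no modifications.

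**The concern.** The code and the text name different predictors for the same analysis. The text asks how exposure varies with a measure of liver function. The code regresses log exposure on `clcr`, which is not among the markers named in the text and is not defined in either document. The name suggests creatinine clearance.

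At stake is the supplementary description of exposure across the range of hepatic function, and the fitted line on the planned plots. If `clcr` is not in the analysis dataset, the step stops and the slip is found at once. If a variable of that name does exist, the step runs without complaint and reports a slope, a 90% interval and an R-squared for a relationship the plan never set out to estimate. The second case is the worse one because nothing flags it.

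**Working it through.** No sample size, power or event figure is involved, so the check compares the text with the code.

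**Step 1. Is the code meant for this regression?** Each element of the code is set against SAP 6.1 and Protocol 9.3.2.3.

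| Element | Text | Code in SAP Appendix 2 | Agree? |
|---|---|---|---|
| Response | PK parameters, eg AUCinf, AUClast, Cmax | `l&var` (log PK parameter) | Yes; the text states no scale for the regression |
| Slope and intercept | May be reported | `ParameterEstimates` output | Yes |
| Interval level | 90% | `clb alpha=0.1`, and 1 − 0.1 = 0.90 | Yes |
| R-squared | May be reported | `FitStatistics` output | Yes |
| Predictor | Hepatic function, eg albumin, PT, T bili | `clcr` | **No** |

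This is the only PROC REG code in the SAP, and the plan describes no other linear regression of PK parameters on a continuous measure. The code therefore belongs to this analysis, and the predictor is the one element that disagrees.

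**Step 2. Could `clcr` be a hepatic marker under another name?** It occurs once in the two documents, in this line. The only clearance term in the SAP's abbreviation list is CL/F, "apparent clearance". The nearest term in the protocol's list is eCrCl, estimated creatinine clearance, which is a kidney measure. Nothing links `clcr` to albumin, PT or bilirubin.

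**Step 3. Could a renal predictor be intended?** The protocol uses kidney function as an eligibility limit (5.2.1, criterion 7) and for safety monitoring (Appendix 7). In both places the measure is CKD-EPI eGFR, not creatinine clearance. Protocol 4.2 expects the kidney to contribute little to elimination of the drug. Neither document plans a regression on renal function, and SAP 2.1 declares no change of predictor.

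**Step 4. How many fits are affected?** Assume the code is run for the three PK parameters given as examples.

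- As coded: 3 parameters × 1 predictor (`clcr`) = 3 fits, of which 3 × 0 = 0 are on a hepatic marker.
- With one hepatic marker substituted: 3 × 1 = 3 fits, all on a hepatic marker; change in number of fits 3 − 3 = 0.
- With all three named markers, one per model: 3 × 3 = 9 fits.

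**Step 5. Does it reach the primary analysis?** The group comparison has its own code (PROC MIXED with hepatic function group as the only fixed effect), and `clcr` does not enter it. The effect on the Test/Reference ratios is nil.

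**The case against.** The strongest reply is that no method has been chosen wrongly. The text of both documents is correct and consistent, the code is offered only as an example, and the regression itself is optional. A programmer who reads SAP 6.1 would put in the right marker, and the printed code is a template in any case, since `&var` has to be supplied before it runs. All of this stands, and it keeps the point small.

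Four further points against the criticism also stand, in whole or in part:

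- That `clcr` is undefined proves little by itself. Other program variables in the same code, such as `subjid`, are not defined either. The weight rests on the mismatch with SAP 6.1.
- That `clcr` means creatinine clearance is inferred from the name.
- The markers and PK parameters are given as examples, so no single marker is fixed and the count of three fits is an assumption.
- SAP 2.1 is not contradicted, because a slip in example code does not modify the plan. It shows only that no change of predictor was declared.

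The reply does not remove the mismatch. `clcr` is a literal variable name, not a placeholder of the kind the code uses for the response. The appendix is the SAP's only programming specification for this regression, and the line is complete, with no sign of redaction or damage.

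**Conclusion.** The concern holds and is minor. The example code does not fit the regression that SAP 6.1 and Protocol 9.3.2.3 describe. Taken literally it gives no estimate of the relationship between exposure and hepatic function, nor the fit needed for the line on the planned plots. The harm arises only if the line is used without being checked against SAP 6.1, and its form depends on whether the dataset holds a variable called `clcr`, which the documents do not show. The mismatch itself rests on no assumption. The primary ANOVA, its 90% intervals and the sample size are untouched.

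**What to change.** In the MODEL statement of the PROC REG example, replace `clcr` with the hepatic function marker or markers the sponsor selects from those in SAP 6.1, one marker per model, for example `model l&var=albumin / clb alpha=0.1;`.

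The cost is one variable name in one line. Albumin, total bilirubin and PT are already among the safety laboratory tests in Protocol Appendix 2, Table 6, so no new data are needed and the text of SAP 6.1 can stay as it is. The number of models does not rise if one marker is used.

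Two clarifications could be made at the same time, though neither is part of the error: whether the marker value comes from screening or from Day 1 before dosing, and that the regression is on the log scale, as the code implies but the text does not state.
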